8.2.4.4 Dose Reduction Levels Based on Lenalidomide Maintenance Starting Dose

The daily dose of lenalidomide in maintenance may be reduced successively by one level from the starting dose. There will be no more than one dose level reduction from one Cycle to the next unless otherwise permitted after consultation with the medical monitor. No dose (re)escalation is permitted at any time.

Subjects who cannot tolerate the lowest applicable dose level are to be discontinued from the Treatment Phase.

The daily oral dose of study drug shall be reduced by one level (refer to Table 5) at the next treatment Cycle if toxicity requiring dose modifications (as in Section 8.2.4.2; Table 2) has occurred during the previous treatment Cycle.

Table 5:Dose Reduction Steps for Adverse Events Related to Study Drug for
Subjects Initiating Maintenance Treatment at 10 mg Daily on Days
1 to 21, Every 28 Days

Dose	Once Daily on Days 1-21, Every 28 Day Cycles
Level 1 (starting dose)	10 mg daily on Days 1-21, every 28 days
Level 2 ^a	5 mg daily on Days 1-21, every 28 days
Level 3 ^a	2.5 mg daily on Days 1-21, every 28 days
Level 4 ^{a, b}	2.5 mg every other day on Days 1-21, every 28 days

^a Once a subject's dose has been reduced, no dose re-escalation will be permitted unless discussed with medical monitor.

^b Subjects who cannot tolerate Dose Level 4 are to be discontinued from the Treatment Phase of the study.

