This Phase 3b multicenter, randomized, open-label study will enroll subjects with relapsed/refractory follicular lymphoma grades 1-3b, transformed follicular lymphoma, marginal zone lymphoma or mantle cell lymphoma. All subjects enrolled will receive 12 cycles of lenalidomide plus rituximab induction therapy.

The study is designed to compare the efficacy and safety of two maintenance regimens following the induction therapy. Subjects who have stable disease (SD), partial response (PR), unconfirmed complete response (CRu) or complete response (CR) at the end of 12 cycles of induction therapy will be randomized to one of two maintenance arms: Arm A (experimental) or Arm B (control). Subjects randomized to Arm A will receive lenalidomide plus rituximab combination maintenance therapy (for 18 cycles) followed by optional lenalidomide single-agent maintenance (to progression). Subjects randomized to Arm B will receive rituximab single-agent maintenance (for 18 cycles).

Subjects will be stratified at time of randomization to the maintenance arm by histology, lines of anti-lymphoma therapy, and age.

The overall study design is described in Figure 1. The study is divided into a Screening Period, a Treatment Period (induction and maintenance), and a Follow-up Period. Approximately 500 subjects are planned to be enrolled.

Upon giving written informed consent, a subject will enter the Screening Period and undergo safety and other assessments to determine eligibility for the study. All Screening assessments must be completed within 28 days prior to the subject initiating induction therapy.

Subjects enter the Induction Treatment Period at the time they complete screening procedures and meet all eligibility criteria. Eligible subjects entering the Induction Treatment Phase will be enrolled using an Interactive Voice Response System (IVRS). The treatments will be given as described in detail in Section 8 and must begin no later than 1 week after enrollment in IVRS to receive induction therapy. Cycle length during induction and maintenance is 28 days.

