Safety will be monitored throughout the study. Safety evaluations will include adverse event (AE) reporting, second primary malignancies (SPM) reporting, physical examinations, vital sign measurements, concomitant medications/procedures, and clinical laboratory safety tests. All AEs and concomitant medications will be assessed and recorded from the time informed consent is obtained.

Second primary malignancies will be monitored as events of interest and should be included as part of the assessment of AEs throughout the course of the study. Investigators are to report any SPM as SAEs regardless of causal relationship to the study drug[s], occurring at any time for the duration of the study, from the time of signing the informed consent document (ICD) for 5 years from the date the last subject initiated induction therapy.

Dose modification rules and rules for discontinuation due to toxicity are outlined in Section 8. Subjects who discontinue treatment due to toxicity will enter the Follow-up Period.

Once the 114 PFS events are confirmed, the follow-up period will continue for 5 years after the last subject has initiated induction therapy, and all subjects who are in the follow-up period will be deemed as completed and will be off boarded from the study

TABLE OF CONTENTS

TITLE PAG	GE	1
OVERALL	RATIONALE FOR PROTOCOL AMENDMENT 5:	6
SUMMAR	Y OF KEY CHANGES FOR PROTOCOL AMENDMENT 5	6
PROTOCO	L SUMMARY	8
TABLE OF	F CONTENTS	12
LIST OF T	ABLES	16
LIST OF F	IGURES	17
1	INTRODUCTION	18
1.1	Follicular Lymphoma	18
1.1.1	Therapy in Relapsed/Refractory Follicular Lymphoma	19
1.2	Mantle Cell Lymphoma	20
1.2.1	Therapy in Relapsed/Refractory Mantle Cell Lymphoma	21
1.3	Marginal Zone Lymphoma	21
1.3.1	Therapy in Relapsed/Refractory Marginal Zone Lymphoma	22
1.4	Lenalidomide	22
1.5	Preclinical Studies of Lenalidomide and Rituximab in Lymphoma	23
1.6	Clinical Studies of Single-Agent Lenalidomide and Rituximab plus	
	Lenalidomide in FL, MZL, and MCL	24
1.6.1	Follicular Lymphoma	24
1.6.2	Marginal Zone Lymphoma	27
1.6.3	Mantle Cell Lymphoma	27
1.7	Lenalidomide as Maintenance Therapy	29
2	STUDY OBJECTIVES	31
2.1	Primary Objective	31
2.2	Secondary Objectives	31
		31
3	STUDY ENDPOINTS	32
3.1	Primary Endpoint	32
3.2	Secondary Endpoints	32
		32
4	OVERALL STUDY DESIGN	33
4.1	Study Design	33
4.1.1	Screening Period	33
4.1.2	Induction and Maintenance Period	33
4.1.3	Enrollment in Induction Treatment Period	33
4.1.4	Randomization to Maintenance Treatment Period	34

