4.1.4 Randomization to Maintenance Treatment Period

After 12 cycles of lenalidomide plus rituximab induction therapy, subjects achieving CR/CRu, PR or having SD will be randomized to enter the maintenance period. During the maintenance period, subjects randomized to Arm B will receive rituximab (only) administered for 18 Cycles. Subjects randomized to Arm A will receive lenalidomide plus rituximab treatment for 18 Cycles and then lenalidomide until relapse or progression of disease. Lenalidomide (only) treatment in Arm A will be given per subject and/or physician discretion as described in detail in Section 8 and must begin no later than 1 week after the last cycle of rituximab plus lenalidomide. Subjects randomized under previous protocol (version 16 January 2014) who achieve a response of SD or better at the end of the Induction Treatment Period will remain in their originally assigned arm of maintenance therapy.

All subjects (in both Induction and Maintenance Treatment Periods) receive treatment as described unless they withdraw consent from treatment, experience unacceptable toxicities or have disease progression. Once subjects discontinue or complete treatment, they enter the follow-up period. All enrolled subjects will be followed for disease progression using the schedule described in Table 1. Subjects who progress before the end of planned treatment will enter the Follow-up Period. Determination of disease progression will be based on investigator assessment. All subjects who discontinue the protocol-specified treatment early for any reason without documented evidence of disease progression will also be followed in the Follow-up Period.

All subjects who will be on treatment upon reaching 5 years after the last subject has initiated induction therapy will continue the treatment and will be followed up for safety purposes only.

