8 DESCRIPTION OF STUDY TREATMENTS

8.1 Description of Investigational Product(s)

Investigational products in this study are lenalidomide and rituximab.

Celgene Corporation will supply lenalidomide 2.5 mg, 5 mg, 10 mg, 15 mg, and 20 mg capsules for oral administration. Subjects will receive treatment with lenalidomide for 21 days per Cycle.

Study drug will be packaged in bottles containing study capsules for days 1 - 21 of every 28 day Cycle.

Commercially available intravenous (IV) formulation of rituximab may be used.

In Germany, Celgene Corporation will supply both lenalidomide capsules and rituximab intravenous formulation as investigational products.

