NCI CTCAE Toxicity Grade ^a	ACTION REQUIRED
Grade 3 neutrophil count decreased (neutropenia) (one time reading)	• Follow CBC at least every seven days
Neutrophil count decreased (Neutropenia) Sustained (≥ 7 days) Grade 3 OR ≥ Grade 3 associated with fever (temperature ≥ 38.5° C) OR Grade 4	 Hold (interrupt dose). Follow CBC at least every seven days If neutropenia has resolved to ≤ Grade 2, restart at next lower dose level Use of growth factors (G-CSF, GM-CSF) is permitted as per ASCO and ESMO guidelines
Platelet count decreased (Thrombocytopenia) ≥ Grade 3 (platelet count < 50,000 cells/mm ³ [50 x 10 ⁹ /L])	 Hold (interrupt dose) Follow CBC weekly If thrombocytopenia resolves to ≤ Grade 2 restart at next lower dose level

Table 2:Dose Modification for Lenalidomide

CC-5013-NHL-008 Amendment 5 Final: 11 Sep 2022

NCI CTCAE	ACTION REQUIRED
Toxicity Grade ^a	
Rash	• Determine the causative study drug(s)
Grades 1-2	
	• Start supportive measures ^b if Grade 2
	No dose adjustment
Grade 3 (Non-desquamating or	• Hold (interrupt dose)
non-blistering)	Start supportive measuresb
	• Evaluate at least weekly
	• If rash resolves to \leq Grade 1 restart at next lower dose
Grade 4 ^c	Discontinue lenalidomide
	Dermatology evaluation
	Consider supportive measuresb
Desquamating (blistering) rash	Discontinue lenalidomide
Any Grade ^c	Dermatology evaluation
	Consider supportive measuresb
Stevens-Johnson Syndrome or	Discontinue lenalidomide
Toxic epidermal necrolysis	Dermatology evaluation
Allergic reaction or hypersensitivity	• Determine the causative study drug(s)
Grade 2	• Hold (interrupt) dose. Follow at least every seven days
	 When the toxicity resolves to ≤ Grade 1 restart at next lower dose level
Grades 3-4	Discontinue lenalidomide
Constipation	
Grades 1-2	Initiate bowel regimen and maintain dose level
> Grade 3	Hold dose and initiate bowel regimen
	 When the toxicity resolves to ≤ Grade 2 restart at next lower dose level
Venous thrombosis/embolism ≥ Grade 3	• Hold (interrupt) dose and start anticoagulation; restart at investigator's discretion (maintain dose level)
Peripheral Neuropathy	Hold (interrupt dose)
Grade 3	• When toxicity resolves to ≤ Grade 1 or to Screening, restart at the next lower dose
Grade 4	Discontinue lenalidomide.

|--|

NCI CTCAE Toxicity Grade ^a	ACTION REQUIRED
Tumor Flare Reaction (TFR) ^a Grades 1-2	Continue lenalidomide, maintain dose level

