8.2.4.3 Dose Reduction Levels Based on Lenalidomide Starting Dose

The daily dose of lenalidomide may be reduced successively by one level from the starting dose. There will be no more than one dose reduction from one Cycle to the next. No dose (re)escalation is permitted at any time unless as specified in Table 4.

Note, rituximab dosing should continue as per protocol even if lenalidomide has been discontinued due to toxicity.

Subjects who cannot tolerate the lowest applicable dose level are to be discontinued from the Treatment Phase.

For subjects with a starting dose of 20 mg daily on Days 1 to 21 every 28 days (for subjects with a creatinine clearance ≥ 60 mL/min), the daily oral dose of study drug shall be reduced by one level (a decrement of 5 mg; refer to Table 3) at the next treatment Cycle if toxicity requiring dose modifications (as in Section 8.2.4.2) has occurred during the previous treatment Cycle.

Subjects who have moderate renal insufficiency [creatinine clearance $\geq 30 \text{ mL/min}$ but < 60 mL/min (refer to dose reduction steps in Table 4)]:

- Will receive a lower starting dose of study drug of 10 mg once daily (Days 1 to 21 of 28 days) in Cycle 1 and Cycle 2
- If the subject remains free of drug-related Grade 3 or 4 toxicities for at least 2 Cycles, the dose may be increased to 15 mg once daily on Days 1 to 21 of a 28-day Cycle at the discretion of the treating physician from Cycle 3 onwards
- The daily oral dose of study drug may be reduced successively by one level in response to an event of toxicity as described in Table 2

Table 3:Dose Reduction Steps for Adverse Events Related to Study Drug for
Subjects Initiating Treatment at 20 mg Daily on Days 1 to 21, Every
28 Days

Dose	Once Daily on Days 1-21, Every 28 Day Cycles
Level 1 (starting dose)	20 mg daily on Days 1-21, every 28 days
Level 2 ^a	15 mg daily on Days 1-21, every 28 days
Level 3 ^a	10 mg daily on Days 1-21, every 28 days
Level 4 ^{a, b}	5 mg daily on Days 1-21, every 28 days

^a Once a subject's dose has been reduced, no dose re-escalation will be permitted unless discussed with medical monitor.

^b Subjects who cannot tolerate Dose Level 4 are to be discontinued from the Treatment Period of the study.

Table 4:	Dose Modification Steps for Subjects Initiating Treatment at 10 mg
	Daily on Days 1 to 21, Every 28 Days

Dose	Once Daily on Days 1-21, Every 28 Day Cycles
Level -1 ^a	15 mg daily on Days 1-21, every 28 days

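### In maintenance, the lenalidomide stop rule read literally also ends rituximab, in Arm A only, contrary to the protocol's own note that rituximab continues

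*Combined protocol and SAP*

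**What the plan says.** Two adjacent sentences in Section 8.2.4.3, the starting-dose section, bear on this. The first reads "Note, rituximab dosing should continue as per protocol even if lenalidomide has been discontinued due to toxicity". The second reads "Subjects who cannot tolerate the lowest applicable dose level are to be discontinued from the Treatment Phase". The footnotes to Tables 3 and 4 repeat the second rule.

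For maintenance, Section 8.2.4.4 repeats the removal sentence. Table 5 footnote b applies it to the last step, 2.5 mg every other day: "Subjects who cannot tolerate Dose Level 4 are to be discontinued from the Treatment Phase of the study". The rituximab note does not appear in that section.

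Three other places fix what leaving treatment means:

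- The Protocol Summary (Study Design) divides the study into screening, "a Treatment Period (induction and maintenance), and a Follow-up Period".
- Section 8.1 states: "Investigational products in this study are lenalidomide and rituximab".
- The Protocol Summary (Overview of Safety Assessments) states: "Subjects who discontinue treatment due to toxicity will enter the Follow-up Period".

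**The concern.** A subject who cannot tolerate the lowest lenalidomide level has stopped lenalidomide for toxicity, so both sentences of Section 8.2.4.3 apply, and they give opposite answers on rituximab. In maintenance a site sees only the removal rule next to the dose table, and must decide whether a note placed in the starting-dose section carries over.

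The primary comparison is lenalidomide plus rituximab against rituximab alone, so rituximab is the backbone both arms share. Arm B takes no lenalidomide and cannot trigger the rule. If sites follow its letter, some Arm A subjects receive less rituximab than controls, and the contrast is no longer purely the addition of lenalidomide. If sites differ, the delivered regimen depends on the site. A result near the null would then be harder to interpret.

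**Working it through.** **1. Can the texts be reconciled?**

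| Place | Rituximab after intolerance of the lowest lenalidomide level |
|---|---|
| 8.2.4.3, note | continues |
| 8.2.4.3, next sentence; Tables 3 and 4 footnotes | subject leaves treatment |
| 8.2.4.4; Table 5 footnote b | subject leaves treatment; no note |
| 8.2.4.5 (rituximab adjustment) | silent |
| 12.1 (reasons for stopping) | silent on one drug or both |

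Table 2 in Section 8.2.4.2 has events whose action is "Discontinue lenalidomide", such as Grade 4 neuropathy. One could confine the note to those events and the removal rule to failure at the lowest level. The text does not draw that line, and toxicity as worded in the note covers both.

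**2. Doses at stake.** Maintenance rituximab is given on Day 1 of Cycles 13, 15, 17, 19, 21, 23, 25, 27 and 29, which is 9 doses.

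- *10 mg starter, one level per cycle (Table 5):* 10 mg in Cycle 13, 5 mg in 14, 2.5 mg in 15, 2.5 mg every other day in 16. A stop in Cycle 16 loses Cycles 17, 19, 21, 23, 25, 27 and 29, which is 7 doses.
- *Entering at 2.5 mg:* Section 8.2.3 keeps subjects already below 10 mg at their current dose, and Table 4 goes down to 2.5 mg. Such a subject has 2.5 mg in Cycle 13 and 2.5 mg every other day in 14. A stop in Cycle 14 loses Cycles 15 to 29, which is 8 doses.
- *Average (assumption: 10 mg starters, stops spread evenly over Cycles 16 to 30):* doses lost are 7, 6, 6, 5, 5, 4, 4, 3, 3, 2, 2, 1, 1, 0, 0. The sum is 49, and 49/15 = 3.27.

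After Cycle 30 there is no rituximab left to lose.

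**3. Base power.** Section 10.3 gives 92% power at a hazard ratio (HR) of 0.533, described as 20% better than assumed, so the design HR is 0.533/0.8 = 0.666. The Schoenfeld formula is power = Φ(√d/2 × |ln HR| − 1.96). With d = 114 and HR 0.666 it is Φ(5.339 × 0.406 − 1.96) = Φ(0.208) = 58.2%, against about 57.9% stated. At HR 0.533 it gives 91.9%, against 92% stated.

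**4. Illustration only.** The documents give neither a stop rate nor the effect of missing rituximab. The simulation assumes:

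- 157 subjects per arm, uniform entry over 63 months, and a control median of 51.5 months;
- analysis at the 114th event, one-sided 0.025, interim look ignored, 12,000 runs per scenario (Monte Carlo SE at most 0.5 points);
- stops in Arm A uniform over Cycles 16 to 30, after which the hazard equals control;
- if rituximab also stops, the hazard is m times control from the first missed dose to the end of Cycle 30.

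| Arm A stopping | Rituximab continues | Stops, m = 1.5 | Stops, m = 2 |
|---|---|---|---|
| none | 57.2% | – | – |
| 5% | 53.9% | 53.5% | 52.3% |
| 10% | 51.4% | 49.0% | 47.3% |

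At 10% stopping the HRs are 0.688, 0.695 and 0.702. The part due to rituximab is 0.4 to 1.6 points at 5% stopping and 2.4 to 4.1 points at 10%. Most of the fall from 57.2% comes from stopping lenalidomide, which happens under either reading.

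**5. Timing.** Cycle 29 Day 1 is 28 × 28 = 784 days, or 25.8 months, after first dose. Adding 63 months of accrual gives 88.8 months, against 105 months to the primary analysis.

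**The case against.** The strongest reply is that the clash and its consequence sit in different sections. The contradictory sentences are in 8.2.4.3. Induction is common to all subjects and precedes randomization, so a conflict there cannot unbalance the arms. Section 8.2.4.4 carries one rule. If the note reaches maintenance, rituximab is already protected. If it does not, the rule is clear and stopping the whole Arm A regimen is a design choice.

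That narrows the point without removing it. The text does not say whether the note reaches maintenance, so two sites can act differently in good faith. On the literal reading, the rule takes the shared backbone from one arm, against the intent the note expresses.

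Other parts of the reply stand:

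- *Follow-up is kept.* Section 4.1.4 says that subjects who stop early "without documented evidence of disease progression will also be followed in the Follow-up Period", and Section 10.2 analyses subjects by assigned arm. A reader might infer a false-positive risk or lost PFS events from the rule. The documents do not support that: less rituximab in Arm A works against Arm A.
- *The power figures are assumption-driven.* At 5% stopping with m = 1.5 the difference is within simulation error.
- *Reporting.* A reader might infer that planned summaries would hide the imbalance. Section 10.7 plans study drug exposure by study period without saying whether it is split by drug. The protocol also refers to a separate Statistical Analysis Plan. A gap inferred from silence is not established.
- *Same wording in induction.* Applying the rewording to 8.2.4.3 would be harmful on its own. Section 8.3 randomizes after 12 induction cycles with stable disease or better. A lenalidomide-intolerant subject could finish induction on rituximab alone, be assigned to Arm A and enter the ITT population after one maintenance dose.

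**Conclusion.** The inconsistency is real, and for maintenance it should be corrected. It is minor. The firm result is the number of doses exposed: up to 7 of 9 for a 10 mg starter stepping down one level per cycle, and up to 8 for a subject entering at 2.5 mg. Seven is not a protocol ceiling. Section 8.2.4.4 also allows larger reductions after consultation with the medical monitor.

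The direction is dilution toward the null, with possibly inconsistent site practice, and there is no type I error risk. The size of the effect on PFS cannot be derived from the documents. The simulated power differences rest on an assumed stop rate, hazard multiplier and control median, and should not be quoted as an estimate for this trial. A reader might also take the rule as evidence that Arm A was under-treated, but nothing in the documents shows that any subject was affected.

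**What to change.** In Section 8.2.4.4 and Table 5 footnote b, replace the removal sentence with: 'Subjects who cannot tolerate the lowest lenalidomide level permanently discontinue lenalidomide; rituximab continues through Cycle 29 per Section 8.2.2 unless rituximab itself is not tolerated.'

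Do not carry this wording into Section 8.2.4.3 or Tables 3 and 4 unless the protocol also states that subjects who stopped lenalidomide for intolerance during induction are not randomized.

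For subjects already treated, an optional descriptive table would show maintenance rituximab doses received (of 9) by arm, and doses given after lenalidomide was discontinued. It needs no new visits or tests.

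The cost is one sentence and one footnote, plus the IRB/EC approval that Section 14.5 requires for an amendment. With the last rituximab dose near month 89, the wording may reach few or no subjects, so it is best folded into an amendment made for other reasons.

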8.2.4.5 Dose Adjustment for Rituximab

The dose of rituximab will be interrupted and modified according to the clinical practice of the investigator's institution, and in line with the approved prescribing information, including administration, warnings, precautions, contraindications, and adverse reactions, as applicable.

In case a dose is missed during the Cycle because of toxicity, it will not be rescheduled. In case of delay in the start of the next Cycle due to toxicity, rituximab of the next Cycle will be postponed until the AE has resolved, at which point the next Cycle is started.

8.3 Method of Treatment Assignment

Enrollment into the Induction Treatment Period will occur in the Screening Period, once all the required Screening procedures have been completed and subject meets all eligibility criteria, and all required data have been submitted to the IVRS/ Interactive Web Response System (IWRS) system. Upon completion of 12 cycles of induction therapy and achieving a response of PR or CR/CRu or having SD, the maintenance treatment will be randomly assigned using the IVRS. Subjects randomized under previous protocol (version 16 January 2014) who achieve a response of SD or better at the end of the Induction Treatment Period will remain in their originally assigned arm of maintenance therapy.

- Subjects will undergo randomization in a 1:1 ratio to either Arm A (maintenance therapy as rituximab plus lenalidomide followed by optional lenalidomide) or Arm B (maintenance therapy as rituximab). The randomization procedure will be accomplished by a validated interactive voice response system (IVRS/IWRS).
- Randomized subjects will be stratified by:
 - Histology (FL (grades 1-3b and transformed FL) versus MZL versus MCL)
 - Lines of anti-lymphoma therapy ($\leq 2 \text{ vs.} > 2 \text{ lines}$)
 - Age (< 65 vs. \geq 65 years)

